1.1 Background and rationale

This statistical analysis plan (SAP) serves to describe the methods and time points of the statistical analysis performed for the randomized controlled trial TARGET-READ phase 2 (transition care intervention targeted to high-risk patients to reduce readmission).

1.2 Objectives

The primary objective is to evaluate the effect of a transitional care intervention (“TARGET” intervention) prioritized to higher-risk medical patients on the composite of 30-day unplanned readmissions and death.

Secondary objectives are to evaluate:

- the effect of a targeted transitional care intervention to higher-risk medical patients on hospital utilization, medication adherence, patient’s perspective on quality of transition of care and time to readmission or death (whatever comes first),
- the effect of a targeted transitional care intervention on the primary outcome in subgroup population of patients with intermediate (simplified HOSPITAL score of 4 or 5) compared to high risk of readmission (simplified HOSPITAL score ≥ 6), who suffer from common chronic diseases (diabetes, chronic heart failure, COPD or cancer), and according to living place, living status and health insurance,
- the cost-effectiveness of the transitional care intervention.

2 Study methods

2.1 Trial design

The study is a national multicenter single-blinded randomized controlled trial.

2.2 Randomization

Allocation of patients is done when all inclusion and exclusion criteria are satisfied. Patients are randomly assigned in a ratio of 1:1 to one of two treatment arms:

- 1) Transitional care (intervention) or
- 2) Usual care (control).

Allocation of patients is done with the data management system (REDCapTM) that also hosts the electronic case report forms (eCRFs). Allocation is stratified by:

- Discharge site (Hôpital Fribourgeois, Centre hospitalier Bienne, CHUV Lausanne, Hôpital neuchâtelois)
- Readmission risk category according to the simplified HOSPITAL score (intermediate vs high risk, i.e. a HOSPITAL score of 4 or 5 vs ≥ 6)

The readmission risk category is documented on eCRF “Eligibility” by variable `strat_1`, the discharge site is coded via the patient ID. The random allocation is performed centrally within the data management system using permuted block with random block sizes of 2, 4 and 6. Investigators receive the allocation only after the eCRF “Eligibility” has been completed. The allocation is documented by variable `alloc_a_group` on eCRF “Eligibility”.

2.3 Sample size

Because we will target patients at higher risk of readmission, we hypothesize that the intervention could reduce the relative risk of readmission by 25%, i.e. more than the 18% reduction found in a recent meta-analysis where patients were mostly not at high risk for readmission. Based on previous findings, the expected 30-day readmission and death rate for patients at intermediate or high risk according to the simplified HOSPITAL score is around 27%. Allowing for 10% loss to follow-up, we determine that we will need 1,380 patients for the study to have 80% power, i.e. 690 in each arm.

The intervention phase (randomized controlled trial) will be restricted to the eligible patients who are at intermediate to high risk of 30-day readmission according to the simplified HOSPITAL score, i.e. $\geq 4/13$ points. We estimate to have around 18,000 patients discharged during the 20-month study period, 30% of which (5,400) will be at higher-risk for a 30-day readmission or death. This should be enough to reach the targeted sample size within the study time frame.

2.4 Stratification

Unless explicitly mentioned, all primary analyses will be stratified for the factors used at randomization (section 2.4).

CTU Bern	SAP for TARGET-READ phase 2	05.03.2019
	Version 1.0	Page 6 27

2.5 Statistical interim analyses and stopping guidance

There is no interim analysis planned, i.e. there are no stopping rules on the individual or trial level.

2.6 Timing of final analysis

All outcomes will be analyzed collectively after study completion. After completion of data entry, data validation and cleaning will be performed. Data analysis will start after database lock.

2.7 Timing of outcome assessments

Table 1: Timing of outcome assessments

Assessment	Index hospitalization ¹⁾		Follow-up ²⁾ (post-discharge)		
	Pre-study screening	Screening (before inclusion)	Visit 1 (inclusion, day 0)	Visit 2 (day 3 ±1)	Visit 3 (day 14 ±1)
Demography	X				
Eligibility	X				
HOSPITAL score	X				
Informed consent		X			
Randomization		X			
Baseline characteristics		X			
Medical history		X			
Medication		X			
Activity of daily living (ADL Katz score)		X			
Exposition to intervention		X	X	X	
Medication discrepancy			X	X	
Adverse drug event			X	X	
Primary outcome: unplanned readmission or death					X
Secondary outcomes:					
Number of unplanned readmission					X
Number of days of hospitalization within 30 days					X
Diagnoses at readmission or cause of death					X
Number of emergency department visits					X
Number of PCP visits					X
Discharge satisfaction (3-CTM)					X
Costs of readmission					X

1) Assessment based on electronic health record and/or in person.

2) Assessment by phone call

CTU Bern	SAP for TARGET-READ phase 2	05.03.2019
	Version 1.0	Page 7 27

2.8 Blinding

Most of the study personal including PI, study nurses, statistician and data manager will not be blinded. However, the study nurses collecting the outcomes or working on data cleaning will be blinded to the group allocation.

3 Data management

The CRFs in this trial are implemented electronically using a dedicated electronic data capturing (EDC) system (REDCap, <https://www.project-redcap.org/>). The EDC system is activated for the trial only after successfully passing a formal test procedure. All data entered in the CRFs are stored on a Linux server in a dedicated mySQL database. Responsibility for hosting the EDC system and the database lies with CTU Bern.

3.1 Data export

At final analyses, data files will be extracted from the database and imported into a statistical software package according to the SOP for data preparation and programming².

3.2 Data validation

First line data validation is performed by the online eCRF system at real-time as defined in the data dictionary. Second line data validation and cleaning will be performed after completion of data entry but before database lock according to the SOP for data validation³.

All baseline characteristics (section 5.5), procedural characteristics (section 5.6) and variables used to derive the outcomes (section 6.2) will be checked for completeness and for outliers. Dates will be checked for consistency (e.g. sequence of date of discharge, intervention phone calls and outcome assessment). The time between discharge and intervention phone calls and outcome assessments will be calculated and values outside the visit windows will be checked.

4 Statistical principles

4.1 General

All recorded and derived variables will be presented by treatment group (and visits, if appropriate) using descriptive summary tables. Continuous variables will be summarized by mean and standard deviation, or median and lower and upper quartiles. Categorical variables will be summarized by absolute and relative frequencies.

In all summaries, the treatment groups will be displayed in the following order: transitional care, usual care. For all parameters, baseline is defined as the last available pre-treatment value (i.e. the last non-missing value available before randomization).

The data collected from patients who are not randomized will only be used for the patient's disposition.

4.2 Confidence intervals and p-values

A level of statistical significance of 5% will be used. All statistical testing will be two-sided. All tests will be accompanied by an effect measure (transitional care vs usual care) with a 95% confidence interval (95% CI).

4.3 Adherence and protocol deviations

Major protocol deviations are

- Violation of inclusion or exclusion criteria
- No informed consent signed
- Crossing-over to the other treatment arm
- Patients not discharged home or to nursing home
- Patients not discharged alive
- Change of HOSPITAL score risk group between inclusion and patient discharge
- Not receiving post-discharge component of the intervention and at least one of the follow-up phone calls (unless the patient was readmitted or died before the follow-up phone call).
- Blindness breach

These protocol deviations will be summarized by treatment group using absolute and relative frequencies.

Table 2: Derivation of protocol deviations.

Protocol deviation	eCRF sheet	Variable	Variable type	Derivation
Violation of inclusion or exclusion criteria				
Adult patient	Baseline Characteristics	patient_age	Continuous: years	patient_age<18
Planned discharge home or nursing home	Eligibility	discharged_alive_home	Binary: No, Yes	discharged_alive_home==No
Patient expected to be discharged alive?	Eligibility	discharged	Binary: No, Yes	discharged==No

CTU Bern	SAP for TARGET-READ phase 2	05.03.2019
	Version 1.0	Page 10 27

Protocol deviation	eCRF sheet	Variable	Variable type	Derivation
Hospital stay of at least 24 hours	Baseline Characteristics	computed_nbdays	Continuous: days	computed_nbdays>=1
Patient at higher risk of 30-day readmission (HOSPITAL score ≥ 4)	Eligibility	hosp_score_simple	Integer: 0-12	hosp_score_simple<4 or hospital_change==Yes & hosp_score_simple_2<4
Patient at higher risk of 30-day readmission (HOSPITAL score ≥ 4)	Baseline Characteristics	hospital_change	Binay: No, Yes	
Patient at higher risk of 30-day readmission (HOSPITAL score ≥ 4)	Baseline Characteristics	hosp_score_simple_2	Integer: 0-12	
Previous enrolment into the current study	Eligibility	already_enrolled	Binay: No, Yes	already_enrolled==Yes
Not living in the country in the next 30 days	Eligibility	home_ch	Binay: No, Yes	home_ch== No
No phone to be reached at.	Eligibility	phone	Binay: No, Yes	phone== No
Not speaking French or German (depending on the site)	Eligibility	lang	Binay: No, Yes	lang== No
Informed consent	Eligibility	consent_signed	Binay: No, Yes	consent_signed==no
Crossing-over to the other treatment arm	Protocol Violation	category_interv_notdone category_interv_1funotdone category_interv_2funotdone category_interv_crossover	Binay: No, Yes	(category_interv_notdone==Yes & category_interv_1funotdone==Yes & category_interv_2funotdone==Yes) or category_interv_crossover==Yes
Not discharged home or nursing home	Baseline Characteristics	discharged_destination	Categorical: Home, Nursing home, Other acute care Hospital, Acute geriatric, Rehab, Palliative care, Other, Unknown	discharged_destination!=Home & discharged_destination!=Nursing home
Not discharged alive	Baseline Characteristics	discharged_alive	Binay: No, Yes	discharged_alive==No
Change of HOSPITAL score risk group between inclusion and patient discharge	Eligibility	hosp_score_simple	Integer: 0-12	hospital_change==Yes & hosp_score_simple==4 or 5 & hosp_score_simple_2 > 6
Change of HOSPITAL score risk group between inclusion and patient discharge	Baseline Characteristics	hospital_change	Binay: No, Yes	
Change of HOSPITAL score risk group between inclusion and patient discharge	Baseline Characteristics	hosp_score_simple_2	Integer: 0-12	or hospital_change==Yes & hosp_score_simple>6 & hosp_score_simple_2==4 or 5
Not receiving post-discharge component of the intervention and at least one of the follow-up phone calls	Protocol Violation	category_interv_notdone	Binay: No, Yes	category_interv_notdone==Yes or (reach_phone_d3==No & reach_phoned_14==No)
Follow-up calls	Follow-up calls	reach_phone_d3, reach_phone_d14	Binary: No, Yes	
Blindness breach	Protocol Violation	description	Free text	Includes "blind"

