4.4.2 Per-protocol set (PPS)

The PPS consists of all subjects in the FAS who received the allocated treatment and did not have any major protocol deviations (section 4.3).

5 Trial Population

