6.1 Outcome definition

6.1.1 Primary outcome

The primary outcome is the number of patients who have an unplanned readmission or die within 30 days after discharge.

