6.2 Outcome derivation

Table 8: Derivation of primary and secondary outcomes.

Outcome	eCRF sheet	Variable	Variable type	Derivation	Outcome type
Primary: Unplanned readmission or death within 30 days after discharge	Baseline Characteristics	discharged_alive	Binary: No, Yes	discharged_alive==No or	Binary
	Follow-up calls	reas_pat_notre_d3, reas_pat_notre_d14	Categorical: Death, No answer, Other	reas_pat_notre_d3==Death or	
	Outcomes 30 days	death_d30	Binary: No, Yes	reas_pat_notre_d14==Death or	
Deaths within 30 days after discharge	Baseline Characteristics	unplanned	Integer: 0-6	death_d30==Yes or	Binary
		discharged_alive	Binary: No, Yes	unplanned>=1	
		reas_pat_notre_d3, reas_pat_notre_d14	Categorical: Death, No answer, Other	discharged_alive==No or	
Outcomes 30 days	Follow-up calls	death_d30	Binary: No, Yes	reas_pat_notre_d3==Death or	Binary
		reas_pat_notre_d14	Categorical: Death, No answer, Other	reas_pat_notre_d14==Death or	

Outcome	eCRF sheet	Variable	Variable type	Derivation	Outcome type
Unplanned readmission within 30 days after discharge	Outcomes 30 days	unplanned	Integer: 0-6	unplanned>=1	Binary
Time to first unplanned readmission or death	Baseline Characteristics	disch_date_index, baseline_death	Date: dmy	Time: min(30, min[baseline_death, date_death_d3, date_death_d14, date_death_d30 unplanned_in_1, lcontact_date] – disch_date_index)	Time-to-event
	Follow-up calls	date_death_d3, date_death_d14	Date: dmy		
	Outcomes 30 days	date_death_d30, unplanned_in_1	Date: dmy		
	End of Study	lcontact_date	Date: dmy	Failure: Primary==Yes	
Main cause of readmission or death	Follow-up calls	cause_death_d3, cause_death_d14	Free text	Tabulated free text fields will be manually categorized	Categorical
	Outcomes 30 days	dx_read30, cause_death_d30	Free text		
Number of unplanned hospital readmissions	Outcomes 30 days	unplanned	Integer: 0-6	-	Count
Number of planned hospital readmissions	Outcomes 30 days	planned_readmission	Integer: 0-8	-	Count
Total number of unplanned days of hospitalizations	Outcomes 30 days	unplanned_x_in, unplanned_x_out	Date: dmy	unplanned_x_out – unplanned_x_in	Count
Total number of planned days of hospitalizations	Outcomes 30 days	tot_rehosp_days_planned	Continuous: days	-	Count
Number of emergency room visits	Outcomes 30 days	nb_edvisits	Integer	-	Count
Number primary care provider visits	Outcomes 30 days	nb_pcpvisits	Integer	-	Count

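### The per-protocol set drops patients who die before discharge, whom Table 8 counts as primary events, so it selects on the outcome, and the full analysis set and per-protocol set count different deaths under one name

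*SAP*

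**What the plan says.** **Exclusion.** Section 4.4.2 restricts the PPS to patients who received the allocated treatment and "did not have any major protocol deviations". The list in section 4.3 includes "Patients not discharged alive", which Table 2 derives as "discharged_alive==No". Section 6.3.2 analyses all outcomes in the PPS.

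**Outcome.** In Table 8 (section 6.2) the derivation of the primary outcome opens with "discharged_alive==No or", and the derivation of 30-day death uses the same condition. The time-to-event derivation also takes in a date `baseline_death`. Section 6.1.1, by contrast, states: "The primary outcome is the number of patients who have an unplanned readmission or die within 30 days after discharge".

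**Eligibility score.** Section 2.2 says "Allocation of patients is done when all inclusion and exclusion criteria are satisfied". Table 2 nevertheless flags an inclusion violation when "hosp_score_simple<4 or hospital_change==Yes & hosp_score_simple_2<4" holds, so a revised score can make an enrolled patient ineligible. A change of risk group, which uses the same revised score, is a separate major deviation.

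**Related rules in Table 2.** A destination other than home or nursing home is a major deviation. So is failure to reach the patient at both phone calls. The bullet in section 4.3 exempts patients who were readmitted or died before the call, but the coded derivation has no such exemption.

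**The concern.** A per-protocol set is meant to remove patients whose treatment or enrolment departed from the plan. Death before discharge is neither. The eligibility criterion is that the patient is expected to be discharged alive, which is a different field (`discharged`) on the Eligibility form with its own line in Table 2. A patient can meet that criterion at inclusion and still die in hospital. Removing that patient selects on the endpoint itself.

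The result is two analyses that carry the same outcome name but count different deaths. A difference between the FAS and PPS results could then reflect adherence or simply the missing deaths, and the reader could not tell which. The 30-day death outcome is affected most directly, because every pre-discharge death disappears from it in the PPS.

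The revised score raises a related but weaker issue. If it was recorded after allocation, excluding on it selects on post-randomisation status, though not on the outcome. Its components include the last haemoglobin and sodium before discharge and the length of stay (Table 4), all of which can change during the stay.

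**Working it through.** **1. The planning figures (section 2.3).** Usual-care risk 27%, relative reduction 25%, so the transitional-care risk is 0.27 × 0.75 = 0.2025 and the risk difference (RD) is -6.75 points. With a two-sided 5% level, 80% power, pooled variance and no continuity correction, n = 621 per arm. Allowing for 10% loss, 621 / 0.90 = 690 per arm, or 1,380 in total. The plan's figure reproduces and is not in dispute.

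**2. The same value used twice.**

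| Place | Use of `discharged_alive==No` |
|---|---|
| Section 4.3, Table 2 | Major deviation, so excluded from the PPS under 4.4.2 |
| Section 6.2, Table 8 | Primary event and 30-day death |
| Section 6.1.1 | Outside the stated window, which starts at discharge |

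The first two rows mean that every such patient is an event in the FAS and none can be an event in the PPS.

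**3. Size.** Let e be the FAS event risk in an arm and q the proportion of that arm who die before discharge. All of these are events, so

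PPS risk = (e - q) / (1 - q).

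The SAP gives no q. The values below are assumptions; 0.5% to 3% of 690 is about 3 to 21 patients per arm.

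| q transitional | q usual | PPS risk transitional | PPS risk usual | PPS RD (points) |
|---|---|---|---|---|
| 0.5% | 0.5% | 19.85% | 26.63% | -6.78 |
| 1% | 1% | 19.44% | 26.26% | -6.82 |
| 3% | 3% | 17.78% | 24.74% | -6.96 |
| 1% | 2% | 19.44% | 25.51% | -6.07 |
| 2% | 1% | 18.62% | 26.26% | -7.64 |

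For the fourth row: (0.2025 - 0.01)/0.99 = 0.1944 and (0.27 - 0.02)/0.98 = 0.2551, so RD = -0.0607. The shift from -6.75 is 0.68 points. With equal deaths of 1% the shift is only 0.07 points.

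If there were no effect in the FAS (27% in both arms), 1% under transitional care against 2% under usual care would give 0.2626 - 0.2551 = +0.75 points in the PPS.

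**4. Would dropping the one rule be enough?** No. A patient who died in hospital has neither permitted destination, so the destination rule could still exclude that patient. The calls are recorded for the transitional-care group only (section 5.6), so the phone-call rule can act in that arm alone. If only the phone-call rule caught these deaths, with q = 1% in each arm, the RD would be 0.1944 - 0.27 = -7.56 points. That is further from -6.75 than the -6.82 under the current symmetric rule.

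**5. Timing of the revised score.** Section 4.3 places the change of risk group between inclusion and discharge, and the score sits on the form that also records discharge status and destination. Both point to a time after allocation. Against this, section 5.5.2 describes changes from screening to baseline, Table 1 puts baseline characteristics in the pre-inclusion column, and section 4.1 defines baseline as the last value before randomisation. The SAP does not settle the matter.

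**The case against.** The strongest reply is that Table 8 is at fault and the PPS rule is right. Section 6.1.1 counts events after discharge, a patient who dies in hospital never enters that window, and so the exclusion fits the written endpoint. This is a fair reading, but it moves the error without removing it: Table 8 would then count events in the FAS that the definition leaves out. The `baseline_death` date in the time-to-event derivation suggests that counting these deaths was deliberate. Either way the passages conflict and the two sets count different deaths.

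A second reply is that the numbers are small. That stands where in-hospital deaths are few and balanced. A shift near 0.7 points needs unequal in-hospital mortality, for which the SAP gives no evidence.

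A third is that any per-protocol set conditions on what happened after randomisation. That is true, and it tempers the point about the revised score. It does not cover an exclusion made on the endpoint itself, and section 4.3 accepts as much when it exempts patients who died or were readmitted before a call.

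A reader might go further and infer that the exclusion biases the primary result, that the PPS is the trial's formal check on the FAS, or that the revised score certainly postdates randomisation. The SAP does not support these. Section 6.3.1 puts the primary analysis on the FAS, the PPS is listed under secondary analyses and apart from the sensitivity analyses, and the timing of the score is ambiguous.

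**Conclusion.** The point holds for the PPS. One field and value both defines a primary event and removes the patient from the PPS, and this follows from the SAP's own derivations with no outside assumption. Separately, section 6.1.1 and Table 8 disagree on whether deaths before discharge are events at all; that conflict concerns the outcome definition in both sets.

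The effect of the exclusion is confined to the secondary PPS analyses and is probably small for the composite. Its size rests entirely on assumed in-hospital death rates. The part about the revised score is conditional: it applies where that score was recorded after allocation, and no size can be given for it. This should be corrected before analysis, but it does not threaten the primary FAS comparison.

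**What to change.** 1. Reconcile section 6.1.1 with Table 8: state whether deaths before discharge are events, and apply that one definition in both the FAS and the PPS.
2. If they remain events:
   - remove the deviation for patients not discharged alive from section 4.3 and Table 2;
   - apply the destination deviation only to patients discharged alive;
   - code into the Table 2 phone-call derivation the exemption that section 4.3 already states, so that deaths are not removed by another rule or from the intervention arm only.
3. Base PPS eligibility on `hosp_score_simple`, the pre-randomisation score. State when `hosp_score_simple_2` was recorded. Where that was after allocation, report scores below 4 and changes of risk group descriptively and do not exclude on them.

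The cost is SAP wording and several lines of derivation code, with no new data. The small downside is that the PPS keeps a few patients who did not receive the post-discharge component.

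### A change of HOSPITAL risk group between inclusion and discharge counts as a major deviation, so the per-protocol set can exclude eligible patients who were treated as allocated

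*SAP*

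**What the plan says.** On enrolment, SAP section 2.2 states: "Allocation of patients is done when all inclusion and exclusion criteria are satisfied". The allocation is released only once the Eligibility eCRF is complete. Section 2.3 describes the trial as "restricted to the eligible patients who are at intermediate to high risk of 30-day readmission according to the simplified HOSPITAL score", meaning a score of at least 4. Sections 2.2 and 6.3.4 split this range into 4 or 5 versus 6 or more, for stratification and for a subgroup analysis.

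On deviations, section 4.3 lists "Change of HOSPITAL score risk group between inclusion and patient discharge" as major. Table 2 derives it from the score on the Eligibility eCRF and a second score on the Baseline Characteristics eCRF. A separate Table 2 row, under violations of the inclusion or exclusion criteria, uses "hosp_score_simple<4 or hospital_change==Yes & hosp_score_simple_2<4".

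On consequences, the PPS in section 4.4.2 keeps patients who "received the allocated treatment and did not have any major protocol deviations". Section 6.3.2 repeats the analysis of all outcomes in the PPS. Section 6.3.1 places the primary analysis in the full analysis set (FAS).

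**The concern.** A per-protocol set is meant to show the effect in patients who were properly enrolled and treated as allocated. A move between the intermediate and high groups bears on neither. The patient is eligible on both sides of the boundary, and the SAP describes one intervention and one usual-care arm without distinguishing risk groups.

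The score that triggers the exclusion can also move after allocation. According to Table 4 its components include the last haemoglobin and last sodium before discharge and the length of stay. The exclusion is therefore a selection on a prognostic value that may arise after randomisation. The pre-discharge component is delivered in one arm only (section 5.6), so changes could in principle differ by arm. What is at stake is the interpretation and precision of the PPS results.

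**Working it through.** **1. The plan's own figure, used as the base for step 4.** The inputs are:
- control risk 27% and a 25% relative reduction (section 2.3), so 27% versus 20.25%, a difference of 6.75 points;
- section 4.2: "A level of statistical significance of 5% will be used" and "All statistical testing will be two-sided";
- section 2.3: "Allowing for 10% loss to follow-up, we determine that we will need 1,380 patients for the study to have 80% power".

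With p̄ = 0.23625, the usual formula with pooled variance under the null and no continuity correction gives

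n = [1.960·√(2·0.23625·0.76375) + 0.842·√(0.27·0.73 + 0.2025·0.7975)]² / 0.0675², rounded up to 621 per arm.

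621 / 0.90 = 690 per arm, 1,380 in total. The stated sample size is reproduced and is not in question.

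**2. When the two scores are taken.**
- Section 2.2: the score that decides eligibility and stratum is on the Eligibility eCRF, completed before the allocation is released. Table 1 lists randomisation with the assessments before inclusion.
- Section 4.3: the change is measured between inclusion and discharge. The second score sits on the same eCRF as discharge status and destination.
- Section 5.5.2, Table 4: the text and footnote describe the same change as running from screening to baseline. Section 4.1 defines baseline as the last value before randomisation.

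The wording of section 4.3, the discharge fields on that eCRF and the score components favour a second score taken after randomisation. The SAP is not consistent on this, however.

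**3. Who is excluded.** Applying the Table 2 rules to every pair of inclusion score (4 or more) and later score gives:

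| Inclusion score | Later score | Excluded from PPS as coded? |
|---|---|---|
| 4 or more | below 4 | yes (eligibility row) |
| 4 or 5 | 7 or more | yes (risk-group row) |
| 7 or more | 4 or 5 | yes (risk-group row) |
| 4 or 5 | 6 | no |
| 6 | 4 or 5 | no |

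Each exclusion is triggered by the later score alone. The last two rows are changes of group under section 4.3 that the code misses, because it uses `>6` where the stratum begins at 6. That is a separate inconsistency. Correcting it alone would exclude more of these patients.

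**4. Loss of precision.** The SAP gives no rate of change, so the fractions f are assumed and taken as equal in both arms. The standard error grows by 1/√(1−f) if event rates stay the same. Power uses the step 1 assumptions and starts from 621 evaluable patients per arm.

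| f | Patients (f × 1,380) | 1/√(1−f) | Evaluable per arm | Power |
|---|---|---|---|---|
| 0 | 0 | 1.000 | 621 | 80% |
| 5% | 69 | 1.026 | 589 | 78% |
| 10% | 138 | 1.054 | 558 | 76% |
| 20% | 276 | 1.118 | 496 | 71% |

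**The case against.** The strongest defence is that the score is built on the last values before discharge, so the inclusion score can be read as provisional and the revised one as the intended measurement. Table 4 and Table 9 both use the revised score when it has changed. The inclusion criteria themselves are in the protocol, which is not at hand. A set restricted to patients whose final score confirms the target population is then coherent. This has real force for the row on scores below 4, where one cannot say with certainty that the criterion no longer applied. It has little force for a move between two eligible groups, which leaves the patient in the target population.

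It is also fair that the stakes are limited. Every randomised patient stays in the FAS, deviations are reported by arm, and the SAP states no decision that rests on the PPS.

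Two stronger readings are tempting but not supported:
- *The rule removes higher-risk patients.* This fits upward movers only. Patients who fall from 7 or more to 4 or 5, or below 4, also leave, so the net direction is unknown.
- *The rule creates a false treatment effect of known size.* Suppose there is no true effect, 10% of each arm would change, changers have 40% risk and others 25%. If all changers leave the control arm but only half leave the intervention arm, the remaining risks are 25.0% and (0.90·0.25 + 0.05·0.40)/0.95 = 25.8%, a difference of +0.8 points. This needs half of the intervention arm's would-be changers to stay in the set with their 40% risk, for instance because their changes go unrecorded. If only 5% truly change there and all are excluded, the same inputs give 25.0% and no bias. The SAP offers no evidence of under-recording, and haemoglobin, sodium and length of stay are objective.

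Finally, section 4.3 also excludes patients not discharged alive, or not discharged home or to a nursing home. Removing the risk-group item therefore does not free the PPS of all selection after randomisation.

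**Conclusion.** The point holds for the risk-group item. The PPS excludes patients who were eligible in either group and may have been fully treated as allocated, because of a value that can change after randomisation and does not concern adherence. The certain effects are this selection and some loss of precision: a standard error about 3%, 5% or 12% larger at assumed exclusion rates of 5%, 10% or 20%. The direction and size of any bias cannot be derived from the SAP.

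A reader might infer that the primary result is compromised. It is not, since only the secondary PPS analyses are affected. For the row on later scores below 4 the case is weaker. Judging the criterion at randomisation agrees better with section 2.2, but the alternative is arguable while the timing of the second score is described in two ways. The conclusion assumes that at least some second scores are taken after allocation, which section 4.3 indicates.

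**What to change.** - Remove the change of risk group from the major deviations that define the PPS (section 4.3 and its row in Table 2). Report score changes descriptively by arm.
- Reconcile section 5.5.2 (screening to baseline) with section 4.3 (inclusion to discharge) on when the second score is taken.
- In the Table 2 eligibility row, judge the criterion on the score at randomisation, `hosp_score_simple<4`. Run the `hosp_score_simple_2<4` exclusion as a labelled sensitivity analysis of the PPS.

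This deletes one bullet, edits two rows of Table 2 and needs no new data. The downside is that the PPS keeps some patients whose discharge score differs from their inclusion score.
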